#### 2.2 Phase IIa

The Phase IIa part consists of a single patient cohort. The initiation of the Phase IIa part and the dose level to apply will be determined based on the DLTs and landmark AEs observed in Phase I part and following a review by the ISC of all safety data collected in Phase I. No security time intervals will apply between two consecutive patients.

# 2.3 Number of patients and evaluable patients

The Phase I part of the study will be conducted in a few sites to enroll between 6 and 12 evaluable patients, should no or one dose de-escalation level be applied, respectively.

Evaluable patients for Phase I are patients having completed the DLT period (ending on Day 29) and received all 3 Pexa-Vec intra-tumoral treatments and 2 nivolumab infusions, or having exhibited a DLT.

In the Phase IIa part of the study, the number of participating countries and sites will be expanded to about 3 countries and 10 sites, in order to enroll a total of 30 evaluable patients, including Phase I patients evaluable for Phase II, and comparable in terms of population and treatment regimen (same inclusion/exclusion criteria and same treatment regimen).

Evaluable patients for Phase IIa are patients having received at least 2 administrations of Pexa-Vec and 2 administrations of nivolumab and undertaken at least one post-baseline radiological assessment and/or with any evidence of disease progression other than CT scan.

The maximal number of patients to be enrolled in the Phase I/IIa study may is then 42 evaluable patients. Considering a 10% rate of non-evaluable patients who will have to be replaced for the implementation of principal per protocol analysis, the final maximal patient enrolment in the study would be 47 patients.

#### 3 STUDY OBJECTIVES AND ENDPOINTS

## 3.1 Primary objectives and endpoints

The primary objective of the study is:

- In Phase I: To evaluate the safety profile of intratumoral (IT) Pexa-Vec combined with intravenous (IV) nivolumab in patients with advanced HCC. Corresponding endpoints will consist of (S)AEs graded according to NCI-CTCAE version 4.03, DLTs and landmark AEs
- In Phase IIa: To evaluate the anti-tumor activity and efficacy of IT Pexa-Vec combined with IV nivolumab in patients with advanced HCC. The primary endpoint will be the Overall Response Rate (ORR) according to RECIST 1.1

## 3.2 Secondary objectives and endpoints

# 3.2.1 Secondary objectives

In Phase I, the secondary objective is to assess signals of efficacy.

In Phase IIa, the secondary objectives are to assess safety and signals of efficacy in terms of additional radiological endpoints (all imaging endpoints evaluated by RECIST 1.1), survival and viral load.

## 3.2.2 Secondary endpoints

Both in Phase I and Phase IIa

Disease Control Rate (DCR) at 4 months

Disease Control Rate (DCR)

Time to Progression (TTP)

Duration of Response (DoR)

Progression Free Survival (PFS)

Overall Survival (OS)

Blood viral load (HCV, HBV when appropriate)

Additionally, in Phase I

**ORR** 

Additionally, in Phase IIa

(S)AEs after grading per NCI-CTCAE version 4.03

# 3.3 Exploratory objectives

# 4 STUDY DURATION

This study started in July 2017 (First Patient In). Recruitment is expected to be completed by Feb 2019 and the study is expected to be completed by Feb 2020 (Last Patient Last Visit).

# 5 TREATMENT PLAN

[figure not shown]
#### 5.1 Randomization

No randomization is planned in this study.

## 5.2 Duration of Treatment

Patients of Phase I and Phase IIa will receive intratumoral (IT) injections of Pexa-Vec in combination with nivolumab intravenous (IV) infusions:

- Pexa-Vec injections will be performed on D1, D15 and D29. Additional Pexa-Vec boosts
  may be performed from Week 12 after discussion on a case by case basis between the
  investigator and Transgene, on the grounds of individual patient benefit.
- Nivolumab will be given from D15 every 2 weeks as long as a clinical benefit is observed with no unacceptable toxicity.

# 6 DEFINITION OF THE POPULATIONS TO BE ANALYZED

For Phase I part and safety evaluation, the Safety (SAF) population will be the primary population and the DLT population will be used for decision for de-escalation or continuation for Phase IIa part. DLT population will also be used for secondary endpoints of efficacy.

For Phase II part, the primary dataset will be the Per Protocol population and efficacy analyses will be repeated for Intent-To-Treat population. Safety population will be used for safety evaluation as secondary endpoint.

# 6.1 Subject populations

## Safety population

All patients enrolled into the study who received at least one dose of either IMP will be included in the safety analysis. The patients will be analyzed according to the treatment actually received (Pexa-Vec or Pexa-Vec + Nivolumab) and this population will be the primary dataset for safety evaluation.

## **DLT** population

In Phase I, patients who received all 3 Pexa-Vec and 2 nivolumab administrations and completed the DLT period and/or patients having exhibited a DLT after at least one dose of either IMP will be included in DLT population. The patients will be analyzed according to the treatment actually received and this dataset will be used for safety evaluation.

## Per protocol (PP) population

In Phase IIa, patients without major protocol deviations who received at least 2 administrations of Pexa-Vec and 2 administrations of nivolumab and undertaken at least one post-baseline assessment and/or with any evidence of disease progression other than CT scan will be included in PP population. Comparable patients from Phase I (same inclusion/exclusion criteria and same treatment regimen) without major protocol deviation who received at least 2 administrations of Pexa-Vec and 2 administrations of nivolumab and undertaken at least one post-baseline assessment and/or with any evidence of disease progression other than CT scan will also be included in PP population. The patients will be analyzed according to the treatment planned and this dataset will be the primary dataset for efficacy evaluation.

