#### 3.1.2 Number of centers and patients

The Phase I part of the study will be conducted in about 2 sites not located in the USA. This part would enroll between 6 and 12 evaluable patients, should none or one dose de-escalation level be applied, respectively.

In the Phase IIa part of the study, the number of participating countries and of participating sites will be expanded to about 10 sites, overall, in order to enroll a total of 30 evaluable patients, including evaluable Phase II patients and comparable Phase I patients still evaluable for Phase II, in terms of population and treatment regimen.

The maximal overall number of patients to be enrolled may then be of 42 evaluable patients; taking into account a 10% rate of non-evaluable patients, who will have to be replaced for the implementation of principal per protocol analyses, the final total and maximal patient enrolment in this study would involve 47 patients.

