# 6.6.2 Replacement policy

In Phase I, the patient cohort on which the combination safety is evaluated comprises 6 evaluable patients; a Phase I evaluable patient is the patient who has completed the DLT period, ie undergone all 3 Pexa-Vec IT injections and 2 nivolumab IV infusions or exhibited a DLT. A not evaluable patient in Phase I should be replaced.

In Phase IIa, the patient cohort on which the combination efficacy is evaluated comprises 30 evaluable patients, including comparable patients of the Phase I part (population, treatment regimen); a Phase IIa evaluable patient is a patient having received at least 2 administrations of Pexa-Vec and 2 administrations of nivolumab and undertaken at least one post-baseline radiological assessment or exhibited any evidence of disease progression other than radiological. A not evaluable patient in Phase IIa should be replaced.

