# 11.1 Blood pharmacokinetics of Pexa-Vec

# 11.2 Blood pharmacokinetics of nivolumab

# 11.3 Other laboratory analyses

### 12 STATISTICAL METHODS PLANNED AND SAMPLE SIZE

## 12.1 Determination of sample size

## **Hypothesis**

As the patient survival benefit may be correlated with either radiological response of tumors or/and prolonged stabilization of the disease, the analysis of efficacy will consider ORR as primary endpoint. Sample size justification will use available data on ORR, as such: in a Phase I/II trial, 8/42 (19%) patients with previously treated HCC experienced an objective response when treated with single-agent nivolumab (El-Khoueiry et al., ASCO 2015). Therefore, a response rate of 15%-20% with the combination of Pexa-Vec + nivolumab in these patients would be considered disappointing, while a response rate of 35% or more would be promising and would encourage further study of the regimen in these patients. The null hypothesis for response rate H0 is set at 15%, the alternate hypothesis of efficacy is set at HA=35%, the type I error α is set at 5% one sided and the power is set at 80%.

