#### 12.5 Protocol deviations

Any protocol deviation will be discussed with the Investigator on a case by case basis, and characterized as minor or major. Patients with deviations deemed major cannot be included in per protocol analyzes and should be replaced. Anticipated but not limited major deviations are:

- Failure to complete all 3 IT Pexa-Vec injections and 2 nivolumab IV infusions in the Phase I part, 2 IT Pexa-Vec injections and 2 nivolumab IV infusions in the Phase IIa part,
- No histological confirmation of HCC.
- Previous systemic therapy for HCC,
- Child-Pugh score beyond A, or deteriorated hepatic function beyond score, or advanced cirrhosis diagnosis based on albuminemia, INR, bilirubin blood levels and clinical symptoms: uncontrolled ascites or esophageal varices, etc.
- ECOG PS > 1,
- Prohibited concomitant medications or no withdrawal of anti-hypertensive, anticoagulant or anti-platelet medications within protocol-specified conditions,
- Immunologic deficiency,
- Pregnancy and breast-feeding.

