#### 7 STATISTICAL DESIGN

## 7.1 Sample size determination for Phase IIa part

## Hypotheses

As the patient survival benefit may be correlated with either radiological response of tumors or/and prolonged stabilization of the disease, the analysis of efficacy will consider ORR as primary endpoint. Sample size justification will use available data on ORR, as such: in a Phase I/II trial, 8/42 (19%) patients with previously treated HCC experienced an objective response when treated with single-agent nivolumab (El-Khoueiry et al., ASCO 2015). Therefore, a response rate of 15%-20% with the combination of Pexa-Vec + nivolumab in not previously treated HCC patients would be considered disappointing, while a response rate of 35% or more would be promising and would encourage further study of the regimen in these patients. The null hypothesis for response rate H0 is set at 15%, the alternate hypothesis of efficacy is set at H1=35%, the type I error  $\alpha$  is set at 5% one sided and the power is set at 80%.

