# 7.5 Data Review Meeting

A data review meeting will occur:

- Before analysis for Independent Safety Committee at the end of Phase I
- Before Interim Analysis
- Before final statistical analysis

The purpose of data review meeting will be to discuss the following issues:

- Resolve the last issues in data
- Completeness of data capture and coding
- Presence of non-resolved adverse events

- Action to be taken to any of this above data issues
- Classification of protocol deviations into minor and major deviations
- Allocation of subjects to various analysis populations
- Finalize the statistical analysis plan

Data listings will be produced by CRO before the data review meeting, the list of listings to produce will be defined in agreement with Transgene.

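### Primary ORR and its stopping counts exclude and replace treated patients who miss the 2+2 dose minimum; the all-treated analysis should be primary and the denominator of the 15% null stated

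*SAP*

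**What the plan says.** The per-protocol (PP) population is the primary efficacy set (Protocol 12.3.3 and 12.6; SAP 6 and 8.7). SAP 6.1 admits patients without major deviations "who received at least 2 administrations of Pexa-Vec and 2 administrations of nivolumab and undertaken at least one post-baseline assessment". The sentence continues: non-CT evidence of progression can stand in for the assessment.

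In Phase IIa, failing to complete two Pexa-Vec and two nivolumab administrations is itself listed as a major deviation (Protocol 12.5; SAP 6.2). The Phase I counterpart in SAP 6.2 exempts patients with a DLT. The Phase IIa item has no toxicity exemption.

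Both routes out of the set lead to replacement. Protocol 6.6.2: "A not evaluable patient in Phase IIa should be replaced". Protocol 12.5: "Patients with deviations deemed major cannot be included in per protocol analyzes and should be replaced". Protocol 3.1.2 sizes enrolment "taking into account a 10% rate of non-evaluable patients".

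Nivolumab starts on D15 with the second infusion on D29 (SAP 2.1), so the dose minimum cannot be met before about D29. The decision counts in SAP 7.3.3 and 7.4 apply to 15 and 30 evaluable patients. The efficacy analyses are repeated in an ITT set of everyone given at least one dose (SAP 6 and 6.1).

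SAP 7.5 places "Classification of protocol deviations into minor and major deviations", the allocation of subjects to populations and the finalisation of the SAP at a data review meeting before each analysis.

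**The concern.** Reaching the second nivolumab dose is a post-treatment event. A patient who dies, stops for toxicity or deteriorates before it is removed because of how treatment went, and the place goes to someone who got further. Protocol 6.3.4.2 itself lists drug-related events that require treatment to be discontinued. A Phase IIa patient who follows that rule before the second infusion becomes a major deviator.

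ORR in the remaining patients describes those who completed about the first month, not those who started the combination. It is compared with a fixed 15% null in a single-arm trial, and no control arm undergoes the same selection. The counts are small: at the interim, exchanging one non-responder for a responder moves 3 to 4 (futility to continue) or 5 to 6 (continue to reject).

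**Working it through.** **Inputs.** Null ORR: "The null hypothesis for response rate H0 is set at 15"% (SAP 7.1). Alternative: "the alternate hypothesis of efficacy is set at H1=35"% (SAP 7.1). Error rates: the type I error "is set at 5% one sided and the power is set at 80"% (Protocol 12.1). Looks at 15 and 30 with the counts above (SAP 7.3.3, 7.4). Non-evaluable share d = 10% (Protocol 3.1.2; SAP 2.3); 5% and 20% are assumptions used to show a range.

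**1. The plan's own design.** O'Brien-Fleming-type spending at half information spends 0.0056 at the interim (z = 2.538) and leaves z = 1.662 at the end. With the null variance 0.15 × 0.85 = 0.1275:
- interim efficacy: 0.15 + 2.538 × √(0.1275/15) = 0.384, or 5.76 of 15, so 6;
- final: 0.15 + 1.662 × √(0.1275/30) = 0.258, or 7.75 of 30, so 8;
- Pocock-type beta spending of 0.124 at the interim puts futility at 3.1 of 15, so 3.

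The maximum sample size is 29.4 (stated 30), with power 80.3% at 30. The plan's figures reproduce under the normal approximation. Enrolment also reproduces: 42/0.9 = 46.7, so 47.

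**2. Exact error of those counts, no exclusions.** With X1 the responses in the first 15 and Y those in the next 15,

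P(reject) = P(X1 ≥ 6) + Σ P(X1 = x) · P(Y ≥ 8 − x),

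summing over x = 4, 5 if futility is enforced and x = 0 to 5 if it is not. At 15%:
- enforced: 0.0168 + 0.1156 × 0.1773 + 0.0449 × 0.3958 = 0.0551;
- not enforced: add 0.0192 for x = 0 to 3, giving 0.0743.

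At 35% the same sums give power 78.3% / 87.9%.

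**3. Effect of exclusion and replacement.** Let r be the response rate among excluded patients. Then

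ORR(treated) = (1 − d) · ORR(PP) + d · r.

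With r = 0, ORR(PP) = ORR(treated)/(1 − d), the upper bound when exclusion favours the PP set. If r equals ORR(PP), the two rates agree. At d = 10%, 30 evaluable means 30/0.9 = 33.3 treated, so 8/30 = 26.7% is 8/33 to 8/34, or 24.2% to 23.5%.

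**4. P(reject) under PP**, if 15% is the true all-treated rate and r = 0:

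| d | ORR(PP) | futility enforced | not enforced |
|---|---|---|---|
| 0 | 15.0% | 5.5% | 7.4% |
| 5% (assumed) | 15.8% | 7.0% | 9.4% |
| 10% (planned) | 16.7% | 8.9% | 11.9% |
| 20% (assumed) | 18.8% | 14.7% | 19.4% |

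The plan makes futility non-binding, so type I error should be read from the last column.

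**5. If 15% is an evaluable-patient rate.** PP stays at 5.5% / 7.4%. The matching all-treated null at d = 10% with r = 0 is 0.9 × 15% = 13.5%. The same counts applied to the first 15 and 30 treated then have type I error 3.3% / 4.5%. The matching alternative is 0.9 × 35% = 31.5%, with power 67.0% / 78.0%.

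**The case against.** Four points can be made for the plan.

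- **Not every early failure is removed.** A reader might infer from the dosing clause alone that all early deaths, toxicity stops and missed doses drop out. The documents do not support that. A patient with two doses of each product who progresses without a scan stays in as a non-responder. So does one who misses only the third Pexa-Vec injection, or who stops for toxicity after 2+2 doses and a scan. This limits the concern, in the main, to patients short of 2+2.
- **Excluded patients are not certain non-responders.** Those who stop without progression continue 6-weekly scans and may not receive other anti-cancer treatment (Protocol 6.6.1 and 8.11). Patients removed for eligibility or medication deviations may respond like anyone else. So r = 0 is a worst case.
- **The null may already be an evaluable-patient rate.** The benchmark is 8 of 42 evaluable patients (Protocol 1.1.3.3 and 12.1), while 47 were exposed (Protocol 1.4.1.1.2); 8/47 is 17.0%. A reader might infer that the false-positive rate is necessarily inflated. That does not follow. Equally, the protocol never defines the benchmark's evaluable set or shows that it used a 2+2 rule with replacement, so a like-for-like comparison is not established either.
- **There are safeguards.** The CRO biostatistician defines the deviation list before database export, the expected major deviations are prespecified (SAP 6.2), PP exclusions are reported with reasons (SAP 8.2.2), and ITT results will be shown. A reader might infer that patients are sorted with their responses in view. No section says that response listings go to the data review meeting. The open-label design and the timing of the meeting only leave that possible.

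The ITT repeat does not settle the matter. It carries no decision rule, is not restricted to the Phase IIa regimen or to comparable Phase I patients, and has no rule for a patient without a scan (SAP 7.6 imputes nothing).

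**Conclusion.** The point holds in a limited form. The plan's rule removes treated patients from the primary denominator partly on post-treatment outcome and replaces them, and this can raise ORR relative to all treated patients by a factor of up to 1/(1−d). At the planned 10% the gap at the pass mark is about 26.7% against 24%.

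The effect on the false-positive rate is conditional. It is at most 8.9% / 11.9% against 5.5% / 7.4% at 10% non-evaluable, and only if 15% is an all-treated rate and no excluded patient responds. The 20% figures rest on an assumed rate. If 15% is an evaluable rate that matches this trial's definition, there is no inflation. The documents leave this open, and that is itself a gap.

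The excess over 5% with no exclusions comes from the normal approximation and unenforced futility. It should not be attributed to the PP set.

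**What to change.** - Make the primary ORR analysis all patients given at least one dose at the Phase IIa regimen, including comparable Phase I patients. Count anyone without a confirmed response as a non-responder.
- Apply the interim and final counts to the first 15 and first 30 such patients, with no replacement for efficacy. Reword the interim trigger in SAP 7.3.1 to match. Fixing the number treated matters: keeping 8 responses as the final mark with 33 or 34 treated (interim at 15) gives type I error of 7.3–7.8% with futility enforced and 11.4–12.9% without.
- Keep PP as a supportive analysis.
- State whether 15% and 35% refer to treated or evaluable patients, and restate the operating characteristics: type I error 5.5% / 7.4% and power 78.3% / 87.9% if both are all-treated rates; 3.3% / 4.5% and 67.0% / 78.0% if both are evaluable rates with 10% non-evaluable and none of them responding.
- Finalise the SAP and classify deviations before response data are reviewed.

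**Cost.** No extra patients are needed. It is not a simple swap with the planned ITT set, which lacks the regimen restriction and the non-responder rule. Consistent edits are needed in SAP 2.3, 6, 7.3–7.4 and 8.7 and in Protocol 3.1.2, 6.6.2 and 12.1–12.8. If 35% is an evaluable rate, the stated power falls below the planned 80%, and the plan should say so.

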## Intent-to-treat (ITT) population

All patients enrolled into the study who received at least one dose of either IMP will be included in the intent to treat. The patients will be analyzed according to the treatment planned and this population will be used for efficacy evaluation.

# 6.2 Major protocol deviations

A list of deviations identified by programming and by listing review will be defined by CRO biostatistician according to the Protocol and in agreement with Transgene before the database export. Programs shall be created by the CRO biostatistics team to identify deviations. Furthermore, deviations reported by Data Management and CRAs shall also be taken into account to define the final deviations list of the Study.

# Anticipated but not limited major deviations are:

- Failure to complete all 3 IT Pexa-Vec injections and 2 nivolumab IV infusions in the absence of DLT in the Phase I part, 2 IT Pexa-Vec injections and 2 nivolumab IV infusions in the Phase IIa part,
- No histological confirmation of HCC,
- Previous systemic therapy for HCC,
- Child-Pugh score beyond A, or deteriorated hepatic function beyond score, or advanced cirrhosis diagnosis based on albuminemia, INR, bilirubin blood levels and clinical symptoms: uncontrolled ascites or esophageal varices, etc.
- ECOG PS > 1,
- Prohibited concomitant medications or no withdrawal of anti-hypertensive, anticoagulant or anti-platelet medications within protocol-specified conditions,
- Immunodeficiency,
- Pregnancy and breast-feeding.

GCP deviations (including protocol deviations, applicable SOPs deviations etc) must be tracked. Transgene shall be provided with a deviation listing before the data review meeting. The criticality of each deviation will be established in agreement with Transgene during the data review meeting (at the latest) in order to define the different populations for analyses.

#### 7 STATISTICAL DESIGN

## 7.1 Sample size determination for Phase IIa part

## Hypotheses

As the patient survival benefit may be correlated with either radiological response of tumors or/and prolonged stabilization of the disease, the analysis of efficacy will consider ORR as primary endpoint. Sample size justification will use available data on ORR, as such: in a Phase I/II trial, 8/42 (19%) patients with previously treated HCC experienced an objective response when treated with single-agent nivolumab (El-Khoueiry et al., ASCO 2015). Therefore, a response rate of 15%-20% with the combination of Pexa-Vec + nivolumab in not previously treated HCC patients would be considered disappointing, while a response rate of 35% or more would be promising and would encourage further study of the regimen in these patients. The null hypothesis for response rate H0 is set at 15%, the alternate hypothesis of efficacy is set at H1=35%, the type I error  $\alpha$  is set at 5% one sided and the power is set at 80%.

